Monitoring and Management Plans for Triglyceride Elevations:

Elevated Triglycerides:

Patients may continue to use stable doses of TG-lowering medications during the study. An adjunctive therapy plan is in place for those patients whose TG values meet the protocol-defined threshold criteria. Post-randomization, TG results will be masked to investigators in order to maintain the blind; however, a threshold has been set to notify investigators and provide an opportunity to adjust the patient's standard of care regimen. Beginning at Week 4 (Visit T2), if the TG level exceeds 1000 mg/dL (11.3 mmol/L) while on treatment, the investigator will receive notification from the central laboratory that the patient has met or exceeded the protocol-defined threshold criteria for TG. The investigator will initiate the following plan:

- Any patient with TG >1000 mg/dL (11.3 mmol/L) will be reminded to fast for at least 10 hours and will return to clinic within 1 week for a repeat, fasting TG sample to confirm the TG value

meets the threshold criteria

- Any patient with a confirmed TG >1000 mg/dL (11.3 mmol/L) may initiate standard-of-care therapy (however, gemfibrozil may not be added) to lower TG using a patient-specific prescription. The initiation of this medication will be documented on the case report form as a concomitant medication with the associated start date. These medications will not be provided by the sponsor.
- Patients continuing to exceed the TG threshold after maximizing the standard-of-care triglyceride-lowering therapy will be discontinued from investigational medicinal product (IMP) treatment and will be asked to continue to be followed for safety using the protocol-specified visit schedule.

Monitoring and Management of Potential AEs and Adverse Events of Special Interest (AESI)

Potential AEs:

Based on findings in nonclinical models, potential AEs include reversible hypoglycemia and metabolic acidosis. Potential cases of reversible hypoglycemia and metabolic acidosis will be identified by routine safety monitoring of AEs and clinical safety laboratories.

Musculoskeletal Safety:

Patients with CK abnormalities will also be reviewed for any other lab changes, such as creatinine, and any reported AEs or SAEs. Musculoskeletal events will be identified and evaluated by routine safety monitoring of PE findings and AEs.

Hepatic:

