10.2.11.2. Potential Adverse Events Based on Findings in Nonclinical Models

10.2.11.3. Adverse Events Associated with Other Lipid-Lowering Therapies

Adverse events that are currently monitored for all experimental lipid-lowering therapies and have been associated with previous lipid-lowering therapies and monitoring approach are listed below.

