10.2.11.3.4. Diabetes and Hyperglycemia

Diabetes and Hyperglycemia: New onset diabetes has been associated with the use of statins and is dose related. The product information for statins mentions hyperglycemia increased HbA_{1C} and increases in fasting glucose as potential adverse reactions. Hyperglycemia occurred in 10.8% (n = 10) of the placebo treated patients vs none of the bempedoic acid 180 mg treated patients in the Phase 2 program. Regardless, new onset diabetes through AE monitoring will be captured and summarized for this study and across all of the bempedoic acid studies. Clinical safety laboratories will also be evaluated during the studies including HbA_{1C}, and fasting glucose.

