**19.1.4. ADVERSE EVENTS OF SPECIAL INTEREST (AESI)**

Adverse events of special interest will be identified by pre-specified MedDRA preferred terms provided by Esperion Therapeutics Inc. (see [Appendix 5](#)). These events will be summarized by AESI category, SOC and PT. All AESI will be summarized by severity and relationship to study medication. In addition, AESI will be evaluated by monitoring safety labs as detailed in [section 19.4](#).

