**APPENDIX 5. LIST OF ADVERSE EVENTS OF SPECIAL INTEREST**

Adverse Event Terms per Protocol	Associated MedDRA Preferred Terms
Creatine kinase elevations	Blood creatine phosphokinase abnormal
Creatine kinase elevations	Blood creatine phosphokinase increased
Creatine kinase elevations	Blood creatine phosphokinase MM abnormal
Creatine kinase elevations	Blood creatine phosphokinase MM increased
New onset or worsening diabetes mellitus	Blood glucose abnormal
New onset or worsening diabetes mellitus	Blood glucose increased
New onset or worsening diabetes mellitus	Diabetes mellitus
New onset or worsening diabetes mellitus	Diabetes mellitus inadequate control
New onset or worsening diabetes mellitus	Diabetic ketoacidosis
New onset or worsening diabetes mellitus	Glucose tolerance impaired
New onset or worsening diabetes mellitus	Glucose urine present
New onset or worsening diabetes mellitus	Glycosuria
New onset or worsening diabetes mellitus	Glycosylated haemoglobin increased
New onset or worsening diabetes mellitus	Hyperglycaemia
New onset or worsening diabetes mellitus	Impaired fasting glucose
New onset or worsening diabetes mellitus	Ketoacidosis
New onset or worsening diabetes mellitus	Ketosuria
New onset or worsening diabetes mellitus	Ketosis
New onset or worsening diabetes mellitus	Type 2 diabetes mellitus
New onset or worsening diabetes mellitus	Urine ketone body present
Hepatic disorders	Alanine aminotransferase abnormal
Hepatic disorders	Alanine aminotransferase increased
Hepatic disorders	Aspartate aminotransferase abnormal
Hepatic disorders	Aspartate aminotransferase abnormal
Hepatic disorders	Blood bilirubin abnormal
Hepatic disorders	Blood bilirubin increased
Hepatic disorders	Hepatic enzyme abnormal
Hepatic disorders	Hepatic enzyme increased

Version Number: 1.7  
 Version Date: 21Mar2018

Adverse Event Terms per Protocol	Associated MedDRA Preferred Terms
Hepatic disorders	Hypertransaminasaemia
Hepatic disorders	Liver function test abnormal
Hepatic disorders	Liver function test increased
Hepatic disorders	Transaminases abnormal
Hepatic disorders	Transaminases increased
Hypoglycemia	Blood glucose abnormal
Hypoglycemia	Blood glucose decreased
Hypoglycemia	Hypoglycaemia
Hypoglycemia	Hypoglycaemic coma
Hypoglycemia	Hypoglycaemic encephalopathy
Hypoglycemia	Hypoglycaemic seizure
Hypoglycemia	Shock hypoglycaemic
Metabolic acidosis	Metabolic acidosis
Muscular disorders	Muscular weakness
Muscular disorders	Muscle necrosis

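### SAP Appendix 5 leaves ketoacidosis out of the metabolic acidosis category and counts a glucose term without direction as both diabetes and hypoglycemia (minor; descriptive counts only)

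*SAP*

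**What the plan says.** The protocol synopsis names reversible hypoglycemia and metabolic acidosis as potential adverse events suggested by nonclinical models. It says: "Potential cases of reversible hypoglycemia and metabolic acidosis will be identified by routine safety monitoring of AEs and clinical safety laboratories".

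SAP 19.1.4 then sets the method. "Adverse events of special interest will be identified by pre-specified MedDRA preferred terms", with the terms given in Appendix 5, and "These events will be summarized by AESI category, SOC and PT". Each category therefore has its own place in a planned output. The same section adds that these events will also be evaluated through the safety laboratory results in SAP 19.4.

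Appendix 5 has two columns. The first is headed "Adverse Event Terms per Protocol" and gives the category; the second gives the MedDRA preferred term. Three categories matter here:

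- **Metabolic acidosis:** one term, of the same name.
- **New-onset or worsening diabetes:** 16 terms, among them "Diabetic ketoacidosis" and *Ketoacidosis*.
- **Hypoglycemia:** 7 terms, among them "Blood glucose abnormal", which is also a diabetes term.

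Neither document says which category a term without direction belongs to, how a term listed in two categories is handled, or whether ketoacidosis should also count as metabolic acidosis.

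**The concern.** A category line is read as the number of patients who had that kind of event. Hypoglycemia and metabolic acidosis are two kinds of event that the protocol singles out, so their lines should mean what their labels say.

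As the list stands, a patient with ketoacidosis is counted under diabetes and not under metabolic acidosis. A patient whose event is coded *Blood glucose abnormal* is counted under both diabetes and hypoglycemia, although the glucose value can have been abnormal in only one direction at a time. A reader who looks only at the category lines could conclude that there was no acidosis, or could read a high-glucose event as hypoglycemia (or a low-glucose event as diabetes).

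The stakes are limited to descriptive safety counts. SAP 19 plans no between-group comparison of safety data unless a section says otherwise, and 19.1.4 specifies none.

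**Working it through.** The plan states no figure to reproduce. The check is on how terms map to categories.

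**Step 1: term sets, from SAP Appendix 5.**

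| Category | Number of terms | Shared with another of these categories |
|---|---|---|
| Diabetes | 16 | *Blood glucose abnormal* (with hypoglycemia) |
| Hypoglycemia | 7 | *Blood glucose abnormal* (with diabetes) |
| Metabolic acidosis | 1 | none |

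The diabetes terms that name an acidosis are *Diabetic ketoacidosis* and *Ketoacidosis*. Neither is listed in any other category.

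**Step 2: what one event adds to each line.**

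| Event as coded | Diabetes | Hypoglycemia | Metabolic acidosis |
|---|---|---|---|
| *Ketoacidosis* or *Diabetic ketoacidosis* | +1 | 0 | 0 |
| *Blood glucose abnormal*, value high | +1 | +1 | 0 |
| *Blood glucose abnormal*, value low | +1 | +1 | 0 |

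In the first row the acidosis line is short by one. In the second the hypoglycemia line is too high by one; in the third the diabetes line is. Both categories also contain terms with a clear direction (for example *Blood glucose increased* and *Blood glucose decreased*), so the glucose problem arises only when an event is coded without direction.

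**Step 3: weight of one patient.** The planned arms are 200 on bempedoic acid and 100 on placebo (protocol synopsis; SAP 3.1).

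- Placebo: 1/100 = 1.0 percentage point.
- Bempedoic acid: 1/200 = 0.5 percentage point.

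The documents give no expected number of such events, so no total can be computed.

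**Step 4: after the correction.** Metabolic acidosis goes from 1 term to 1 + 2 = 3. The overlap between diabetes and hypoglycemia goes from 1 term to 0.

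**Step 5: the laboratory side.** The abnormality list in SAP 19.4 has rows for ALT/AST, bilirubin, CK, glucose, HbA1c, creatinine, eGFR and hemoglobin, but none for an acidosis parameter. CO2 is measured (protocol Table 4) and is covered by the by-visit shift tables against normal ranges. Those give low counts a, b and c at Weeks 4, 12 and 24. For these three visits the number of patients ever low is only bounded: max(a, b, c) ≤ ever low ≤ a + b + c.

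**The case against.** The strongest reply is that nothing is lost. Preferred terms are printed beneath each category, and all treatment-emergent events are tabulated by system organ class and preferred term (SAP 19.1.1). A ketoacidosis that leads to admission is a serious event, so it also appears by preferred term in the serious-event summaries (SAP 19.1.3) and in DMC Table 14.3.1.3. Fasting glucose has separate rows at ≤50 and ≥126 mg/dL. The DMC receives chemistry boxplots, and the title of its AESI table, 14.3.1.8, names no category line. All of this stands, and it is why the point is minor.

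It can also be said that both placements are deliberate: ketoacidosis grouped by its cause, and a neutral term placed under both headings for sensitive capture. That is possible, but the SAP does not say so, and a reader of the category line would not know. The protocol also discourages vague AE terms (10.2.9) and asks for a specific diagnosis where possible (10.2.3), so events coded *Blood glucose abnormal* may be few. That limits the size of the problem and leaves the mapping as it is.

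Two stronger readings are tempting, and the documents support neither.

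- **Uneven error across arms.** A reader might infer this from Phase 2, where "Hyperglycemia occurred in 10.8% (n = 10) of the placebo treated patients vs none of the bempedoic acid 180 mg treated patients" (protocol 10.2.11.3.4). Those events are already described with a direction, and Appendix 5 has directional terms for them under diabetes alone. Nothing in the documents gives the share of glucose events coded without direction, and it could be zero.
- **A missed nonclinical signal.** A reader might infer that ketoacidosis is the acidosis seen in animals. The section that would say so, "Potential Adverse Events Based on Findings in Nonclinical Models" (protocol 10.2.11.2), has no readable body in the supplied text.

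On CO2, the by-visit shifts already provide coverage and the table shells were not supplied, so it cannot be said that an ever-low count is absent from the planned outputs.

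**Conclusion.** The point holds as a low-severity, cheap improvement. If Appendix 5 is applied as written, the metabolic acidosis line can omit a ketoacidosis, and a *Blood glucose abnormal* event is counted as both diabetes and hypoglycemia whatever its direction. Each affected patient shifts a line by 1.0 point on placebo or 0.5 point on bempedoic acid. Efficacy results, type I error and power are untouched, and no between-arm distortion is shown.

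The conclusion rests on three assumptions. Ketoacidosis is taken to be a form of metabolic acidosis, which is general medical knowledge and is not stated in the documents. A term listed in two categories is taken to count in both, since no rule says otherwise. The effect is claimed only for the final AESI category summaries.

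**What to change.** In Appendix 5:

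1. List *Ketoacidosis* and *Diabetic ketoacidosis* under metabolic acidosis as well as under diabetes, with a footnote stating the double listing.
2. Assign each *Blood glucose abnormal* event to one category by the direction of the recorded glucose, or show it on a separate line if no value is available.

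Optionally, in SAP 19.4, add one row for CO2 below the lower reference limit at any post-baseline visit. Section 19.1.4 relies on 19.4 for the laboratory evaluation of these events, and its abnormality list has no acidosis parameter.

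The SAP addendum of December 2018 records that the planned analyses are complete and the study unblinded. Present these changes as labelled supplementary outputs, as the addendum already does for post-randomization liver tests, or make them when the term list is next used.

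The cost is a few lines of wording and minor table programming on data already collected. The one drawback is that a ketoacidosis event then appears in two AESI categories, which the footnote explains.

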**19.1.5. MUSCLE RELATED ADVERSE EVENTS**

Muscle related events as reported on the general AE CRF will be summarized by maximum severity and SOC and PT. All muscle related events and details associated with it including cause and location will be provided in a listing.

**19.2. DEATHS**

If any patient dies during the study, as recorded on the Death Event page of the eCRF, the information will be presented in a data listing. Deaths will be categorized as cardiovascular (CV) death (MACE) or non-CV death (non-MACE).

[REDACTED]

Version Number: 1.7  
 Version Date: 21Mar2018

[REDACTED]

### 19.3. CLINICAL ENDPOINTS

Clinical endpoints will be monitored and adjudicated by an independent blinded expert CEC for this study. The following clinical endpoints will be tabulated:

- CV death (MACE)
- Nonfatal myocardial infarction [MI] (MACE)
- Nonfatal stroke (MACE)
- Hospitalization for unstable angina (MACE)
- Coronary revascularization (MACE)
- Non-coronary arterial revascularization (non-MACE)
- Hospitalization for heart failure (non-MACE)
- Non-CV death (non-MACE)

Additional details regarding clinical endpoints and clinical endpoint definitions will be included in CEC charter. The number of incidences and percentage of patients with each positively adjudicated outcome will be presented in a table. Only treatment emergent positively adjudicated events will be presented in the summary table. All adjudicated events will be included in a listing.

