8.3.8. Treatment Week 24/EOS (Visit T5; Day 169 ±7 days)

Patients will undergo the following assessments and procedures at Week 24 (Visit T5):

1. Concomitant medication review (ongoing)
2. Assess AEs, SAEs, and potential clinical endpoints (ongoing)
3. Weight
4. Vital signs
5. Central clinical laboratory evaluations:
 - Hematology, blood chemistry, and urinalysis
 - apoB
 - hs-CRP
 - HbA_{1C}
 - Basic fasting lipids (TC, calculated LDL-C, HDL-C, non-HDL-C, and TG)
 - PK Sample before dose
6. Return of study drug; assessment and recording of dosing adherence
7. IWRS contact to terminate the subject or register completion
8. Physical Exam
9. 12-Lead ECG

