8.4. Early Withdrawal from Study or Treatment

Patients who withdraw from study drug prior to Week 24 (Visit T5) for any reason will be asked to continue to be followed for safety assessments, including basic fasting lipids, at clinic visit following the protocol-specified visit schedule (see [Section 8.3](#)).

Patients who temporarily withdraw from study drug prior to Week 24 (Visit T5) for any reason may restart study drug providing that 1) the patient and the investigator are in agreement regarding this course of action, 2) the patient has been off of study drug for 4 weeks or less; and 3) study drug can be started as soon as possible. For cases where the patient has been off of study drug for more than 4 weeks, the investigator must contact the medical monitor for approval prior to restarting study drug.

Patients who do not wish to continue to return to the clinic for safety assessments will be asked to participate in phone calls from the site at protocol-specified visits (see [Section 8.3](#)), or at a minimum at 24 weeks, to collect information on AEs, concomitant medications, and current health status.

The patient's decision to participate in the clinical study is voluntary. Patients may refuse to continue in the study and/or withdraw from participation in this study at any time, for any reason, specified or unspecified, and without penalty or loss of benefits to which the patient is otherwise entitled.

It is the right and duty of the Investigator to interrupt the treatment of any patient whose health or well-being may be threatened by continuation in this study. Such patients should be withdrawn from the study and should not be continued under a modified regimen.

Patients who are withdrawn from the study may not re-enter. The reasons for withdrawal from this study or treatment may include:

- Patient's withdrawal of consent
- Failure to comply with the protocol
- Lost to follow-up
- Illness, condition, or procedural complication (including AEs) affecting the patient's ability to participate or requiring prohibited medication
- The Sponsor or Investigator terminates the study
- In the Investigator's judgment, it is deemed in the best interest of the patient to discontinue his/her participation in the study
- Any other reason

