Clinical endpoints will be monitored and adjudicated by an independent blinded expert CEC for this study and other ongoing studies the bempedoic acid program. Adjudicated clinical endpoints will be summarized by event type and treatment group. Additional details regarding clinical endpoints and clinical endpoint definitions will be included in CEC charter.

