### 19.1. ADVERSE EVENTS

Adverse Events (AEs) will be coded using MedDRA, Version 20.1.

Treatment emergent adverse events (TEAEs) are defined as AEs that started or worsened in severity after the first dose of IMP (double-blind study medication) and prior to the last dose date of double-blind study medication + 30 days. AEs that occurred on day 1 will be only be determined as TEAE if the site indicated it occurred after first dose on the AE CRF.

See [Appendix 2](#) for handling of partial dates for AEs. In the case where it is not possible to define an AE as treatment emergent or not, the AE will be classified by the worst case, i.e. treatment emergent.

An overall summary of number of subjects within each of the categories described in the subsection below, will be provided as specified in the templates. Listings will include TEAEs and Non-TEAEs.

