## APPENDIX 2. PARTIAL DATE CONVENTIONS

Imputed dates will NOT be presented in the listings.

Algorithm for Treatment Emergence of Adverse Events:

START DATE	ACTION
Known and AESTART=study med start date	If AEPRIOR=Y then not TEAE If AEPRIOR=N then TEAE
Known and AESTART>or < study med start date	If start date < study med start date, then not TEAE If start date > study med start date and <=study med end date + 30 , then TEAE
Partial	If AEPRIOR=Y then not TEAE Otherwise, If Impute 1 st of month if date is missing; impute 1 st of Jan if both date and month are missing. If resulting imputed start date is prior to study med start date, set as study med start date. If imputed start date is <= study med end date + 30 days, then TEAE; otherwise NOT TEAE
Missing	If AEPRIOR=Y then not TEAE Otherwise, Assumed TEAE

Algorithm for Prior / Concomitant Medications:

Please note that the study med start date is the double-blind med start date.

START DATE	STOP DATE	ACTION
Known	Known	If stop date < study med start date, assign as prior If stop date >= study med start date and start date <= end of treatment, assign as concomitant If stop date >= study med start date and start date > end of treatment, assign as post study

START DATE	STOP DATE	ACTION
	Partial	Impute stop date as latest possible date (i.e. last day of month if day unknown or 31 st December if day and month are unknown), then: If stop date < study med start date, assign as prior If stop date >= study med start date and start date <= end of treatment, assign as concomitant If stop date >= study med start date and start date > end of treatment, assign as post treatment
	Missing	If stop date is missing could never be assumed a prior medication If start date <= end of treatment, assign as concomitant If start date > end of treatment, assign as post treatment
Partial	Known	Impute start date as earliest possible date (i.e. first day of month if day unknown or 1 st January if day and month are unknown), then: If stop date < study med start date, assign as prior If stop date >= study med start date and start date <= end of treatment, assign as concomitant If stop date >= study med start date and start date > end of treatment, assign as post treatment

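### The by-arm table of adjudicated cardiovascular events stops 30 days after last dose, so later events in patients followed off drug appear only in a listing

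*SAP*

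**What the plan says.** SAP 19.3 lists the eight adjudicated endpoint types to be tabulated and then narrows the table: "Only treatment emergent positively adjudicated events will be presented in the summary table". The rest are covered by one further sentence: "All adjudicated events will be included in a listing".

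SAP 19.3 does not define treatment-emergent for a clinical endpoint. The only definition is the adverse-event one. SAP 19.1 starts it after the first double-blind dose and closes it "prior to the last dose date of double-blind study medication + 30 days"; the date algorithm in SAP Appendix 2 closes it at "<=study med end date + 30".

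The protocol is wider. Section 11.7 states: "Adjudicated clinical endpoints will be summarized by event type and treatment group". It mentions no treatment-emergent limit, and neither does the matching synopsis paragraph, which also plans a summary of investigator-reported endpoints. Protocol 5.2.4 names cardiovascular event rates as a safety endpoint. Under Protocol 8.4, patients who stop drug "for any reason will be asked to continue to be followed for safety assessments, including basic fasting lipids" on the visit schedule, and Sections 8.3.5 to 8.3.8 assess potential clinical endpoints at each contact. Protocol 11.1 lets the SAP prevail on analysis, so the narrower rule governs.

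**The concern.** The trial plans to follow patients for cardiovascular events after they stop drug and to adjudicate those events, and then leaves part of them out of the adjudicated table by arm. SAP 19.3 gives no reason.

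The cut-off depends on something that happens after randomization. Protocol 10.2.11 directs or considers stopping for confirmed falls in hemoglobin, raised transaminases, raised CK and falls in eGFR, and 10.2.11.1 reports small mean hemoglobin decreases and confirmed transaminase elevations in earlier bempedoic acid studies. Stopping could therefore differ between arms in number or timing, and the tabulated observation time would differ with it. The documents do not show that this will happen. The plan simply has no adjudicated table that would reveal it. With a small number of events in view, a count that depends on the window deserves a companion count that does not.

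**Working it through.** The plan states no figure to reproduce: the visible text gives no discontinuation rate and no expected event count. The check is window arithmetic.

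**Inputs from the documents**
- End of planned follow-up: Day 169, from "Treatment Week 24/EOS (Visit T5; Day 169 ±7 days" (Protocol 8.3.8).
- End of window: last dose + 30 days (SAP 19.1, Appendix 2). I use the Appendix 2 boundary, which counts day 30 as inside. The wording in 19.1 puts it outside, a difference of one day.
- Planned arms: 200 and 100 (Protocol 6.2).

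**Assumptions**
- Discontinuation of 5-30%.
- Last-dose day of those who stop uniform over Days 1-168.
- Everyone who stops stays in follow-up to Day 169.

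**Step 1: untabulated days for one patient with last dose on Day s.** U(s) = max(0, 169 - (s + 30)).

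| Last dose | Untabulated days | Days left to Day 169 | Share |
|---|---|---|---|
| Day 1 | 138 | 168 | 82% |
| Day 29 | 110 | 140 | 79% |
| Day 57 | 82 | 112 | 73% |
| Day 85 | 54 | 84 | 64% |
| Day 113 | 26 | 56 | 46% |
| Day 139 or later | 0 | 30 or fewer | 0% |

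**Step 2: average over uniform stopping.** The sum of U(s) is 138 + 137 + ... + 1 = 138 x 139 / 2 = 9,591, and 9,591 / 168 = 57.1 days. The mean time left after stopping is 84.5 days, so 57.1 / 84.5 = 68% of it is untabulated. As a share of 169 days it is 57.1 / 169 = 33.8%.

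**Step 3: share of an arm's planned person-time.** Multiply by the assumed discontinuation rate. The right-hand column puts every stop at Day 29, using 110 / 169 = 65.1%.

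| Discontinuation (assumed) | Uniform stopping | All stop at Day 29 |
|---|---|---|
| 5% | 1.7% | 3.3% |
| 10% | 3.4% | 6.5% |
| 20% | 6.8% | 13.0% |
| 30% | 10.1% | 19.5% |

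**Step 4: expected omitted events, both arms together.** With uniform stopping, untabulated time is 300 x 0.05 x 57.1 / 365.25 = 2.3 patient-years at 5% and 300 x 0.30 x 57.1 / 365.25 = 14.1 at 30%. At assumed rates of 1-5 events per 100 patient-years, this gives 2.3 x 0.01 = 0.02 to 14.1 x 0.05 = 0.7 events. Averaging one omitted event would need 1 / 14.1 = 7.1 per 100 patient-years even at 30% discontinuation. Only the extreme corner passes one: if 30% stop, all at Day 29, untabulated time is 300 x 0.30 x 110 / 365.25 = 27.1 patient-years, and 27.1 x 0.05 = 1.4 events.

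**Step 5: would late events be captured?** Protocol 10.2.3 and 10.2.7.4 set the routine SAE reporting window to end 30 days after last dose, with later SAEs reported if considered related. Protocol 10.2.9 runs AE recording and SAE reporting to 30 days after the last study visit. For a patient who stops at Day 29 and is followed to Day 169, the first rule ends at Day 59 and the second at Day 199. The visit schedule still asks about potential clinical endpoints, but the two rules give different instructions for the same event.

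**The case against.** A treatment-emergent summary backed by a full listing is an ordinary convention, and it matches the SAP's handling of adverse events. Nothing leaves the report: every adjudicated event is listed, deaths are listed separately as cardiovascular or not (SAP 19.2), and Appendix 1 orders listings by randomized treatment unless a template says otherwise. With few events, a reader could count them by hand. SAP 19 plans no statistical comparison of safety data unless specified, and 19.3 specifies none. All of that stands, and it limits the severity.

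Several stronger readings are tempting, and the documents do not support them:

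- *All events after stopping are lost.* Events within 30 days of last dose stay in the table.
- *This is the only by-arm table of such events.* SAP Appendix 3 also names an investigator-reported MACE table, 14.3.1.15. It is not the adjudicated endpoint, its window is not stated, Appendix 3 is the DMC list, and the table templates are not in the text under review.
- *The restriction destroys the randomized comparison.* Safety outputs use the safety set, grouped by treatment received (SAP 5.1), so the table was never strictly as randomized. What is lost is a full-follow-up comparison by treatment group.
- *One or two events will be missed.* No event rate in the documents supports a count.

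What does not stand is the suggestion that the listing is enough. A listing has no denominators, and the protocol promised a summary by arm for a named safety endpoint.

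**Conclusion.** The point holds at modest severity. The SAP table is narrower than the protocol's planned summary, and its cut-off follows last dose rather than end of study. The SAP describes no unrestricted adjudicated table, and the December 2018 addendum adds none.

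The 2-10% of person-time rests on assumed discontinuation, uniform stopping and complete follow-up. Protocol 8.4 and 8.4.1 allow phone contact or full withdrawal, so for that stopping pattern the figures are upper limits; earlier stopping would raise them. It also rests on reading the adverse-event window into SAP 19.3, which 19.3 does not state. A reader might infer that the truncation is known to favor one arm. The documents give no discontinuation data by arm, so it is a possibility to guard against and no more. The primary efficacy result is not touched.

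**What to change.** 1. In SAP 19.3, keep the treatment-emergent table and state its window for clinical endpoints, resolving the one-day difference between SAP 19.1 and Appendix 2.
2. Add the same table, by treatment group, for all positively adjudicated events from randomization (or first double-blind dose) to end of study.
3. Reconcile the reporting windows in Protocol 10.2.3, 10.2.7.4 and 10.2.9, so that late off-drug events are captured in the same way for every patient. Without this the added table could rest on uneven ascertainment.

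The cost is one more descriptive table from events that are adjudicated anyway, plus the text change on reporting. The downside is that off-drug events may slightly dilute a drug effect in the wider table, which is why the two should be shown together.
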